9.8. UNSCHEDULED VISITS

During the postoperative period, if visit is done for the purpose of medically-indicated follow-up, data from this visit should be recorded on Unscheduled Visit source documents. The need for unscheduled visits is at the investigator's discretion. Specific examinations to be performed at unscheduled visits are also at the discretion of each investigator and are to be recorded on the appropriate section of the source documents.

Data to be collected if deemed appropriate by the investigator may include, but not limited to:

- Uncorrected, distance-corrected or best-corrected visual acuity at far, intermediate or near distance using the high contrast ETDRS chart in the CTS, monocular or binocular
- Manifest refraction
- Corneal Topography
- Intraocular pressure
- Slit-lamp examination for medical findings and other IOL-related findings
- Dilated fundus exam
- Patient-reported visual or ocular symptoms
- Adverse events
- Posterior capsulotomy performed (yes/no)

9.9. DISCONTINUATION OF SUBJECTS

Every attempt must be made to obtain complete follow-up data for all subjects enrolled. It is the responsibility of the investigator to provide complete follow-up data to AcuFocus for each subject. The investigator should notify AcuFocus prior to discontinuing a subject from the study. If a subject is discontinued from the study, the investigator will, if at all possible, have the subject return for a final visit.

Subjects may be discontinued from the study for any of the following:

- At their own request
- In case of any postoperative complication if continued participation in the study has an impact on the safety of any subject
- If irretrievably lost to follow-up for unavoidable reasons such as IC-8 IOL removal/non-IC-8 IOL replacement
- Subject moved/unable to locate
- Subject is uncooperative/refuses to return
- Subject is deceased, ill, unable to travel, or institutionalized

Subjects who plan to be traveling, relocating or otherwise unavailable for postoperative followup visits should not be enrolled in this study. In the event of unplanned subject relocation, efforts should be made by the investigator to collect follow-up information (i.e., general visual acuity from the patient's new physician).

When a subject is discontinued due to IC-8 IOL removal after implantation or failure to implant during the surgery, efforts must be made by the investigator to follow the subject until all ocular adverse events are resolved or stable before exiting the subject from the study.

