9.6.4. SURGICAL COMPLICATIONS

If during the implantation of the IOL, in either eye of the test or the control arm, a surgical complication such as a capsular bag tear/rupture or zonular damage/rupture should occur, the subject should be discontinued from the study. If a surgical complication occurs during the implantation of the investigational IOL, the IC-8 IOL should **not** be implanted. The investigator should treat the subject per routine standard of care and may choose to implant their choice of a back-up, non-investigational, marketed IOL based on the investigator's discretion. The subject

will be discontinued and will be followed by the investigator until the adverse event is considered resolved or stable and then exited from the study.

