If a Nd:YAG capsulotomy is necessary in the IC-8 eye, it is recommended that the YAG capsulotomy be performed around the mask in an omega pattern. This method creates an opening of approximately 10 clock hours around the outside of the mask with 5 to 7 o'clock leaving an inferior hinge. Nd:YAG laser energy has to be titrated to the lowest level to produce a capsular opening. Using an energy that is too high can result in damage to the periphery of the mask. The procedure has to be performed at least one week prior to a postoperative visit; and no sooner than six weeks after surgery for the second eye, unless medically indicated.

Standard manufacturer-recommended procedures should be followed for the eyes implanted with the monofocal or monofocal toric IOLs.

Nd:YAG capsulotomies should be documented on the source document for YAG procedure.

Secondary Surgical Interventions:

Secondary surgical interventions other than Nd:YAG capsulotomies are usually considered to be adverse events.

The study protocol will allow for IOL-related secondary surgical interventions in the following categories upon careful consideration of the risks and benefits:

- IOL repositioning due to IOL placement resulting in an unsatisfactory visual outcome provided placement is believed to be surgically correctable.
- IOL exchange due to incorrect IOL power resulting in an unsatisfactory uncorrected visual acuity.
- IOL exchange due to surgical or postoperative medical complications or adverse events. If the affected eye has been implanted with the IC-8 IOL, a non-investigational IOL must be used for replacement.

If the placement of a monofocal/monofocal toric or IC-8 IOL is repositioned, the patient will continue to be followed through the completion of the study. If an IC-8 IOL is exchanged for a non-investigational IOL, the subject will be discontinued, and will be followed by the investigator until the adverse event is considered resolved or stable and then exit from the study.

Secondary surgical interventions for medical complications may be considered to be in the subject's best interest. Although these procedures are at the investigator's discretion, prior agreement from the medical monitor and AcuFocus is required for any non-emergency secondary surgical procedure. In the case of an IC-8 IOL exchange for refractive error, an FDA waiver must be obtained if desired replacement is another IC-8 IOL.

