18.1. ANALYSIS POPULATION

For the primary effectiveness endpoints, the primary analysis population will be an ITT (Intentto-Treat) analysis. The ITT population includes all subjects who are fully enrolled and are binocularly implanted in the study. For the secondary effectiveness endpoint, the primary analysis population will be a mITT (modified Intent-to-Treat) analysis for all eyes implanted with IC-8 IOL and achieving BCDVA 20/25 or better. For eyes that do not have data available at the 3-, 6- or 12-month visits, data will be imputed according to the imputation methods specified in the SAP.

A Per-Protocol (PP) analysis will also be performed on the primary and secondary effectiveness endpoints to support the primary ITT analysis. The PP population will include eyes from binocularly implanted subjects, evaluated within the proper study interval and without major protocol deviations as determined prior to database lock, and evaluated at least two weeks after any SSIs. Major protocol deviations to be excluded from PP analysis are: those related to inclusion, exclusion or qualification criteria, and/or those that have the potential to either positively or negatively affect the primary and secondary study endpoints, including uncorrected or distance-corrected visual acuities, refraction, contrast sensitivity, and are unrelated to the study procedure or the study device; and they will be specified prior to database lock.

PP analyses will only include available data at the time of analysis (i.e., no data imputation). For the primary effectiveness endpoints, the PP population is usually a subset of the ITT population; for the secondary effectiveness endpoint, the PP population is usually a subset of the mITT population.

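### IC-8 removal is labelled loss to follow-up and ends scheduled assessment, so a removal before month 6 becomes informative missing data in the test group's effectiveness analysis

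*Combined protocol and SAP*

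**What the plan says.** Section 9.9 opens by requiring every attempt at complete follow-up of all enrolled subjects. It then lists reasons for which a subject may be discontinued, one of which is "If irretrievably lost to follow-up for unavoidable reasons such as IC-8 IOL removal/non-IC-8 IOL replacement". The same section tells the investigator to go on following a subject whose IC-8 was removed until ocular adverse events are resolved or stable. It also provides that "If a subject is discontinued from the study, the investigator will, if at all possible, have the subject return for a final visit".

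Section 9.7 (Secondary Surgical Interventions) treats lens events as follows:

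- Repositioning, any study lens: "If the placement of a monofocal/monofocal toric or IC-8 IOL is repositioned, the patient will continue to be followed" to the end of the study.
- Exchange is permitted for complications and for wrong power, the latter worded as "IOL exchange due to incorrect IOL power resulting in an unsatisfactory uncorrected visual acuity". Neither category is confined to one lens type.
- IC-8 exchanged for another type of lens: "If an IC-8 IOL is exchanged for a non-investigational IOL, the subject will be discontinued". Follow-up then runs only until the adverse event is resolved or stable.
- IC-8 exchanged for another IC-8 because of refractive error: "an FDA waiver must be obtained if desired replacement is another IC-8 IOL". No discontinuation is stated.
- Monofocal lens exchanged: no disposition is stated.

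Section 18.1 defines ITT as all fully enrolled, binocularly implanted subjects, so an explanted subject remains in it. It adds: "For eyes that do not have data available at the 3-, 6- or 12-month visits, data will be imputed", by methods given in the SAP. The per-protocol analysis uses available data only. Section 18.2.1 sets the responder criteria at 6 months (1b, 2b, 3b, 4b), and all co-primary endpoints must be met.

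**The concern.** A subject who is still being examined until an adverse event settles is not irretrievably lost. The label also sits badly with Section 10.1, which classes IOL exchange or removal arising from the device's potential risks as an anticipated serious adverse device effect.

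The label matters because of what follows from it. The exit rule stops the scheduled acuity measurements for subjects in whom the lens did not work out, and those values are then imputed. Missingness of this kind depends on outcome. Nothing in Sections 18.1 or 18.2.1 says that an eye without its IC-8 counts as a failure on a responder criterion. If the imputation draws on subjects who kept the lens, an explanted subject is credited with intermediate and near acuity typical of a lens that is no longer in the eye. The criteria are hard thresholds that must all be passed, so a small favourable shift can decide a borderline result.

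**Working it through.** **The plan's own figures.** The plan gives no figure for the effect of removals on effectiveness. The nearest is the attrition allowance in Section 7.0: about 10% attrition and 5% disqualification, with 355 test and 120 control subjects enrolled to complete 300 and 100. Test: 300/(0.90 × 0.95) = 351, or 300/0.85 = 353. Control: 100/(0.90 × 0.95) = 117, or 100/0.85 = 118. The stated figures are reproduced within 3%.

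**How many visual/optical removals a successful trial can contain.** Section 18.3.1, endpoint 3, requires the exact one-sided 95% upper limit to be below 3.1%.

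- n = 300: 4 removals give 3.03% (pass); 5 give 3.47% (fail).
- n = 337 (355 × 0.95, assumed number implanted): 5 give 3.09% (pass); 6 give 3.48% (fail).

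The ceiling is thus 4 to 5, cumulative to 12 months. Removals or exchanges for power or complications fall outside it, so 10 in total is also shown as an assumption.

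**Shift in a responder rate.** If k removals among n subjects are imputed at the retained response rate r rather than counted as failures, the gain is (k/n) × r. Assume r between 50% and 90%, and all removals before month 6.

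| k of n | r = 50% | r = 90% |
|---|---|---|
| 4 of 300 | 0.67 points | 1.20 points |
| 5 of 337 | 0.74 points | 1.34 points |
| 10 of 300 | 1.67 points | 3.00 points |

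**Shift in a mean.** If removed subjects are truly d logMAR worse than imputed, the shift is (k/n) × d. Assume d from 0.1 to 0.5.

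- Smallest, 4 of 300 with d = 0.1: 0.0013.
- 5 of 337 with d = 0.5: 0.0074.
- 10 of 300 with d = 0.5: 0.0167.

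For 4 to 5 removals this is under a tenth of the 0.1 logMAR margin for binocular UCDVA.

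**Can it cross a threshold?** Illustrative rates, with removals counted as failures, n = 300:

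- 50% criterion, retained rate 51%: 0.51 × 296/300 = 50.3% at k = 4; 0.51 × 294/300 = 49.98% at k = 6; 0.51 × 290/300 = 49.3% at k = 10.
- 25% advantage read as percentage points, 70% against 44%: 0.70 × 296/300 − 0.44 = 25.07 points at k = 4; 0.70 × 294/300 − 0.44 = 24.6 points at k = 6.

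Neither example fails at 4 removals; both fail at 6.

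**The case against.** Several stronger readings are tempting, and the documents do not support them.

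- A reader might infer that a control subject whose monofocal lens is exchanged stays in with an improved value while the matching test subject leaves. The protocol does not say so. Only repositioning is expressly said to continue follow-up; the disposition after a monofocal exchange is simply unstated. For wrong power, the IC-8 subject also has the waiver route to another IC-8, with no stated discontinuation. Discontinuation for an intraoperative complication applies "in either eye of the test or the control arm, a surgical complication such as a capsular bag tear/rupture or zonular damage/rupture should occur".
- A reader might infer that the co-primary analyses definitely favour the device. That depends on the SAP's imputation method, which could already treat removals as failures or as worst case.
- A reader might extend a between-arm argument to every 6-month co-primary endpoint. It reaches only binocular UCIVA, UCNVA and UCDVA. DCIVA compares eyes within the test group, although 4b remains a proportion of IC-8 eyes. Depth of focus is assessed at 3 months.
- A reader might infer that removals are hidden in attrition. They are not: visual/optical removals are a co-primary safety endpoint, Section 10.2.1 lists removal and exchange as adverse events, and Section 18.3.3 reports visual/optical removal rates for all four eye groups.

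Two further objections stand. The effect is small, and no example crosses a threshold at 4 removals in 300. Automatic failure on 3b would also be hard to defend: Section 7.3 required the fellow eye to reach 20/32 or better uncorrected, so binocular distance acuity may still meet the criterion.

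What survives is a stated exit rule, not merely a missing detail. The per-protocol analysis is no safeguard, because a subject without a value drops out of it. Nor is the final visit, which is requested only where possible and is not tied to the 160 to 210 day window of the 6-month visit.

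**Conclusion.** The concern holds in limited form. The label in Section 9.9 and the exit rule in Section 9.7, combined with ITT and imputation in Section 18.1, turn IC-8 removals before month 6 into informative missing data in the test group. If the SAP borrows from retained IC-8 subjects, the responder criteria are biased toward the device by roughly 1 point for 4 to 5 removals and up to about 3 points for 10. The effect on means is negligible. These sizes assume response rates of 50% to 90%, acuity deficits of 0.1 to 0.5 logMAR, 300 or about 337 test subjects, and all removals before month 6; the documents give none of these rates or deficits. The result would change only for a criterion within a point or so of its threshold, or within about 3 points if there were 10 removals. The correction is still worth making, because it is cheap and settles in advance how device failures count.

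**What to change.** 1. Section 9.9: remove IC-8 removal or replacement as an example of loss to follow-up, and list IC-8 removal/exchange as a separate, device-related reason.
2. Section 9.7: state one data-collection rule for both arms, so that a subject with any study lens removed or exchanged keeps the remaining scheduled 3-, 6- and 12-month assessments. This also closes the gap on monofocal exchange.
3. Sections 18.1 and 18.2.1: use observed post-exchange values in the ITT mean comparisons and for 3b. For 1b, 2b and 4b, count an eye or subject whose IC-8 was removed without IC-8 replacement before the 6-month visit as a non-responder, instead of imputing from retained subjects. The SAP's imputation section should say the same.

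The split in item 3 is deliberate. Criteria 1b, 2b and 4b ask whether the lens delivers intermediate or near vision, which a removed lens cannot do. Distance acuity after removal can be measured and need not be presumed.

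The cost is protocol and SAP wording, the remaining scheduled visits for a handful of subjects, and slightly less favourable test responder rates (about 1 to 3 points under the assumptions above). Only data collection and analysis change; when a lens should be removed or exchanged is untouched.

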7.0 STUDY POPULATION

Potential study subjects will be recruited from patients with bilateral cataracts who plan to undergo crystalline lens removal by phacoemulsification followed by intraocular lens implantation in the capsular bag. Eligibility for the study will be determined at the preoperative visit. If the patient meets all inclusion/exclusion criteria, he or she must give informed consent to be provisionally enrolled in the study as a subject.

To allow for approximately 10% attrition rate over the duration of the one-year study and another 5% disqualification rate for the first implanted eye, a total of 355 test subjects and 120 control subjects will be consented and provisionally enrolled to ensure 300 test and 100 control subjects are available to complete the one-year follow-up to support the PMA.

Each study site (assuming a total of 23 sites) should enroll approximately 15 subjects in the test group and 5 subjects in the control group, but no more than 25% of the total population of the study. The number of subjects intended to be enrolled in the study for each treatment arm (before

the first implanted eye's qualification to complete enrollment) is shown in **Table 3**. Furthermore, based on previous data from the IC-8 IOL European clinical study, the distribution of preexisting corneal astigmatism between 0 and 1.5 D in the intended population consists of roughly 83-85% of patients between 0 to less than 1.0 D and roughly 15-17% of patients between 1.0 to 1.5 D. The anticipated enrollment ratio is thus approximately 5:1 for < 1.0 D of preoperative corneal astigmatism (Astigmatism Group 1) vs. 1.0 to 1.5 D of preoperative corneal astigmatism (Astigmatism Group 1) vs. 1.0 to 1.5 D of preoperative corneal astigmatism group as shown in **Table 3** should reflect the anticipated enrollment by group in the study. The overall enrollment from all sites will be monitored closely to ensure that the enrollment target should be met for each treatment arm and astigmatism group. When each and all targets are met, the sponsor will inform all sites to cease enrollment. More details on controlling the enrollment process for potential imbalance in baseline characteristics is specified in the Statistical Analysis Plan (SAP).

	Astigmatism Group 1** (< 1.0 D of preoperative corneal astigmatism)	Astigmatism Group 2** (1.0 D to 1.5 D of preoperative corneal astigmatism)

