10.4. ADVERSE EVENT FOLLOW-UP

For every adverse event, appropriate measures should be undertaken to treat and/or monitor the patient until resolution occurs. The investigator should keep AcuFocus closely informed as to the outcome, thereby allowing AcuFocus to comply with the appropriate regulatory reporting requirements. The AE status should be updated on the source documents each time the patient returns for follow-up until resolution of the event. Additionally, the investigator may supply written reports (e.g., from outside specialist evaluations) of the adverse event to AcuFocus. Any subject who is withdrawn from the study due to an adverse event will be followed by the investigator until the outcome is determined to be resolved or stable at which point the subject will be exited from the study.

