For all key safety endpoints, the primary analysis population will be the safety analysis population. The safety population will consist of all subjects who complete enrollment and have been bilaterally implanted and those subjects not successfully implanted with the IC-8 IOL but for whom the IC-8 IOL touched the eye. Safety analyses will only include available data at the time of analysis (i.e., no data imputation). Reporting of cumulative complications (occurring at any time postoperative) will include data from all subjects in the safety population. Test subjects who have undergone the IC-8 IOL surgery with attempted but failed implantation will be followed until all ocular adverse events are resolved or stable before being exited from the study, and they will be counted in the safety population.

The safety population (with no imputation) will also be used for reporting of other postoperatively measured clinical parameters that are not discussed as part of the key effectiveness or safety endpoints.

The primary reporting will be on IC-8 IOL eyes and fellow eyes in the test group or binocular outcomes from both test and control groups. However, key data such as visual acuity, refractive error, medical/lens complications and adverse events will also be reported separately for first and second eyes in the control group.

Besides the ITT (or mITT) and PP populations, key effectiveness outcomes and key safety outcome of BCDVA may also be reported for best-case subjects where appropriate. A best-case subject is defined in ISO 11979-1:2012 as a subject with no preoperative ocular pathology, no macular degeneration detected at any time, and no previous surgery for the correction of refractive errors. In this study, a best-case subject should also have no significant macular pathology at any time. Both eyes must meet the best-case criteria for inclusion in the best-case analysis.

Subjects who are disqualified prior to second-eye implantation will not be counted toward the study cohort or any analysis population. For the disqualified subjects, a listing of UCDVA and BCDVA at preoperative and before study exit will be tabulated, as well as any adverse events; no other analysis will be performed.

In addition to the above analysis populations, additional best-case analyses and exploratory subgroup analyses may also be performed as specified in the SAP.

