As specified in ISO 11979-7:2014, the statistical success criterion is when H_0 is not rejected, i.e. the test result is a p-value greater than 0.05, demonstrating the adverse event rate for the IC-8 eyes is not greater than SPE rate. The statistical success criterion is equivalent to showing the one-sided 95% lower confidence limit of the rate is not greater than the historical control rate based on an exact binomial distribution.

- b. Descriptive statistics (mean, two-sided 90% confidence interval) for the rates of all key adverse events including but not limited to adverse events per ISO 11979-7:2014, adverse events that may be specifically related to the EDOF IOL design, e.g., related to the optical characteristics of the lens, and any other significant ocular adverse events. Summary statistics will be provided for the IC-8 eyes and fellow eyes in the test group, and for first eyes and second eyes in the control group.
- 3. Rate of IC-8 IOL removals due to visual/optical reasons (the rate is based on eyes with events, cumulative through 12 months):

Rate of removals due to visual/optical reasons in the IC-8 IOL eyes is < 3.1%. The one-sided 95% upper confidence limit of the rate (using exact binomial distribution) must be less than 3.1% to claim statistical success.

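### Section 9.9 does not specifically require 12-month lens status for IC-8 subjects who leave with the lens in place, so the co-primary removal rate can miss removals after exit

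*Combined protocol and SAP*

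**What the plan says.** **The endpoint.** Section 18.3.1 item 3 is a co-primary safety endpoint. For IC-8 removals due to visual or optical reasons, "the rate is based on eyes with events, cumulative through 12 months", and for success the "one-sided 95% upper confidence limit of the rate (using exact binomial distribution) must be less than 3.1" per cent. Item 3 does not name a denominator.

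**The population.** Section 18.3 assigns all key safety endpoints to the safety population. Section 18.1 adds "Safety analyses will only include available data at the time of analysis (i.e., no data imputation"), and says that reporting of cumulative complications "will include data from all subjects in the safety population".

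**Attrition.** Section 7.0 allows for "approximately 10% attrition rate over the duration of the one-year study", plus 5% disqualified after the first eye.

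**Follow-up around and after exit.**
- Section 9.9 opens with a general duty on the investigator to obtain complete follow-up data for every enrolled subject.
- It then permits discontinuation at the subject's own request, for refusal to return, and where the subject has moved or cannot be located. A further listed ground is being "irretrievably lost to follow-up for unavoidable reasons such as IC-8 IOL removal/non-IC-8 IOL replacement".
- It also says: "If a subject is discontinued from the study, the investigator will, if at all possible, have the subject return for a final visit".
- After an unplanned relocation, it asks for efforts to collect follow-up information. The example given is visual acuity from the new physician.
- Section 10.4 says: "Any subject who is withdrawn from the study due to an adverse event will be followed by the investigator", until the outcome is resolved or stable.

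None of these provisions names lens status, or a contact at 12 months for a subject who has already left.

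**The concern.** A patient unhappy with vision through a small-aperture lens has a reason to leave the study and a reason to have the lens taken out. If the removal comes after exit and is done elsewhere, the study may never learn of it. The prior-agreement rule for secondary surgery in section 9.7 binds study investigators, not an outside surgeon. Adverse event reporting and the questionnaires mainly reach subjects still being seen.

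On the natural reading of sections 18.1 and 18.3, the eye then stays in the denominator with no event. Every error of this kind lowers the observed rate, so the bias runs one way, in the device's favour. The endpoint involves a handful of events and must be met to claim safety success, so one or two missed removals could decide it.

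**Working it through.** **1. Reproduce the plan's enrolment figure.** Inputs from section 7.0: 300 test completers, 10% attrition, 5% first-eye disqualification.
- 300 / (0.95 × 0.90) = 351, or 300 / 0.85 = 353. The plan states 355, so the planning logic reproduces to within rounding up.

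**2. Expected IC-8 eyes and exits** (derived, not stated in the plan).
- Implanted test eyes: 355 × 0.95 ≈ 337.
- Early exits: 337 × 0.10 ≈ 34. Some of these would be exits because of a known removal, so 34 is an upper figure for subjects leaving with the lens in.
- Completers: 337 − 34 = 303.

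**3. The pass rule.** Exact one-sided 95% upper limit for x removals in n eyes: the 0.95 quantile of Beta(x + 1, n − x). Pass if it is below 3.1%.

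| Removals / eyes | Upper limit | Result |
|---|---|---|
| 5 / 337 | 3.094% | pass |
| 6 / 337 | 3.484% | fail |
| 4 / 336 | 2.703% | pass |
| 5 / 336 | 3.103% | fail |
| 4 / 303 | 2.995% | pass |
| 5 / 303 | 3.438% | fail |

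The cut-off is 5 at 337 eyes and 4 from 336 down to 300. So 337 is the smallest number of eyes at which 5 removals pass, and results at both 337 and 336 are needed. With the count at the cut-off, one unseen removal turns a fail into a pass. The choice of denominator can do the same: 5 removals pass on 337 implanted eyes and fail on 303 completers.

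**4. False-pass chance.** Let f be the share of removals that go unseen. With a true 12-month rate of exactly 3.1%, the chance of passing is P(X ≤ c), where X is binomial with n eyes and probability 0.031 × (1 − f), and c is the cut-off.

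| f (assumed) | n = 337, c = 5 | n = 336, c = 4 |
|---|---|---|
| 0 | 4.9% | 2.1% |
| 5% | 6.7% | 3.0% |
| 10% | 9.0% | 4.2% |
| 15% | 12.0% | 5.8% |
| 25% | 20.4% | 10.8% |

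What the shares mean:
- **f = 5%:** 10% leave evenly over the year, with a constant removal hazard unrelated to leaving. On average half of each leaver's year is unobserved: 0.10 × 0.5 = 0.05.
- **f = 10%:** leavers have the same removal rate as stayers, and none of their removals is seen.
- **f = 25%:** leavers' rate is 0.031 × 0.25 / 0.10 = 7.75% and stayers' is 0.031 × 0.75 / 0.90 = 2.58%, a ratio of three, with every leaver's removal after exit.

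**The case against.** **The plan does seek follow-up.** Section 9.9 requires every attempt at complete data, and in section 14.1 the sponsor monitors patterns of missing data. This stands, and it rules out the stronger reading that nothing is sought after exit. What remains is narrower: the general duty is followed by permitted exits, and no specific step asks for lens status at month 12.

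**Known removals are captured.** A reader might take the section 9.9 wording on loss to follow-up through IC-8 removal as evidence that removals are missed. It is not. Those subjects leave because the lens came out. The removal is a listed adverse event (section 10.2.1), it is reported to the sponsor, and the subject is followed until ocular events resolve or stabilise. Removal leading to exit does not show that exit is followed by hidden removal.

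**The denominator is inferred.** A reader might state as fact that leavers count as lens retained. Item 3 does not say so, and section 18.1 speaks of cumulative complications without naming this endpoint. Sections 18.0 and 18.4 defer further methods, including sensitivity analysis, to a separate SAP that was not available for this review. It may already fix the denominator and the handling of unknown status. It cannot recover lens status that was never collected.

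**337 is the least favourable size nearby.** This stands. Enrolment is capped at 355 and the analysed number is not fixed. With one eye fewer, the false-pass chance stays below 5% even with 10% of removals unseen, so a blanket claim that the test loses its 5% level is not supported.

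**Leavers may be unreachable.** True in part: some who refuse or cannot be located will not answer. Outside records may still settle some cases, and the tipping-point count covers the rest.

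**Conclusion.** The concern holds as a worthwhile, low-cost improvement. The plan does not specifically require 12-month lens status for IC-8 subjects who leave with the lens in place. On the natural reading of sections 18.1 and 18.3 their eyes count as event-free, and any removal after exit is missed in the device's favour.

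The direction of the bias is clear; its size is not. At a true rate of 3.1%, the false-pass chance goes from 4.9% to 6.7–9.0% at 337 eyes, or from 2.1% to 3.0–4.2% at 336, if 5 to 10% of removals are unseen. If 25% are unseen it reaches 20.4% or 10.8%. These shares are assumptions; nothing in the documents supports a particular value. The calculation also assumes that all implanted eyes form the denominator and that the 10% attrition and 5% disqualification occur as planned. The documents do not show that removals will in fact be missed, only that one missed removal can decide the result when the count is at the cut-off.

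**What to change.** Keep the 3.1% limit, the exact test and the prior-agreement rule.

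**Section 9.9.** For every implanted IC-8 subject who exits early for any reason:
- record at exit whether removal has been requested;
- seek lens status at 12 months (in place or removed, date, reason) by telephone or from the treating physician, unless consent to contact is withdrawn.

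**Section 18.3.1 item 3.**
- Name the denominator.
- Count visual or optical removals found through this contact in the primary numerator.
- Report the number of eyes with unknown 12-month status.
- State how many removals among those eyes would turn a pass into a fail.

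If the SAP already covers the denominator and the tipping point, a cross-reference is enough for those items; the contact step still belongs in the protocol.

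**Cost.** One short form, a line in the consent form and about 34 calls or record requests. Reasons given by telephone are less certain than those documented at the site, and some subjects will not be reached. The observed removal rate may rise, and the chance of passing may fall with it.
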